### 13.3 Methods for Evaluation of Measurable Disease

All measurements should be taken and recorded in metric notation using a ruler or calipers. All baseline evaluations should be performed as closely as possible to the beginning of treatment and never more than 4 weeks before the beginning of the treatment.

The same method of assessment and the same technique should be used to characterize each identified and reported lesion at baseline and during follow-up. Imaging-based evaluation is preferred to evaluation by clinical examination unless the lesion(s) being followed cannot be imaged but are assessable by clinical exam.

**Clinical lesions:** Clinical lesions will only be considered measurable when they are superficial (e.g., skin nodules and palpable lymph nodes) and  $\geq 10$  mm diameter as assessed using calipers (e.g., skin nodules). In the case of skin lesions, documentation by color photography, including a ruler to estimate the size of the lesion, is recommended.

**Chest x-ray:** Lesions on chest x-ray are acceptable as measurable lesions when they are clearly defined and surrounded by aerated lung. However, CT is preferable.

**Conventional CT and MRI:** This guideline has defined measurability of lesions on CT scan based on the assumption that CT slice thickness is 5 mm or less. If CT scans have slice thickness greater than 5 mm, the minimum size for a measurable lesion should be twice the slice thickness. MRI is also acceptable in certain situations (e.g. for body scans).

Use of MRI remains a complex issue. MRI has excellent contrast, spatial, and temporal resolution; however, there are many image acquisition variables involved in MRI, which greatly impact image quality, lesion conspicuity, and measurement. Furthermore, the availability of MRI is variable globally. As with CT, if an MRI is performed, the technical specifications of the scanning sequences used should be optimized for the evaluation of the

type and site of disease. Furthermore, as with CT, the modality used at follow-up should be the same as was used at baseline and the lesions should be measured/assessed on the same pulse sequence. It is beyond the scope of the RECIST guidelines to prescribe specific MRI pulse sequence parameters for all scanners, body parts, and diseases. Ideally, the same type of scanner should be used and the image acquisition protocol should be followed as closely as possible to prior scans. Body scans should be performed with breath-hold scanning techniques, if possible.

**PET-CT:** At present, the low dose or attenuation correction CT portion of a combined PET-CT is not always of optimal diagnostic CT quality for use with RECIST measurements. However, if the site can document that the CT performed as part of a PET-CT is of identical diagnostic quality to a diagnostic CT (with IV and oral contrast), then the CT portion of the PET-CT can be used for RECIST measurements and can be used interchangeably with conventional CT in accurately measuring cancer lesions over time. Note, however, that the PET portion of the CT introduces additional data which may bias an investigator if it is not routinely or serially performed.

**Ultrasound:** Ultrasound is not useful in assessment of lesion size and should not be used as a method of measurement. Ultrasound examinations cannot be reproduced in their entirety for independent review at a later date and, because they are operator dependent, it cannot be guaranteed that the same technique and measurements will be taken from one assessment to the next. If new lesions are identified by ultrasound in the course of the study, confirmation by CT or MRI is advised. If there is concern about radiation exposure at CT, MRI may be used instead of CT in selected instances.

**Endoscopy, Laparoscopy:** The utilization of these techniques for objective tumor evaluation is not advised. However, such techniques may be useful to confirm complete pathological response when biopsies are obtained or to determine relapse in trials where recurrence following complete response (CR) or surgical resection is an endpoint.

**Tumor markers:** Tumor markers alone cannot be used to assess response. If markers are initially above the upper normal limit, they must normalize for a patient to be considered in complete clinical response. Specific guidelines for both CA-125 response (in recurrent ovarian cancer) and PSA response (in recurrent prostate cancer) have been published [JNCI 96:487-488, 2004; J Clin Oncol 17, 3461-3467, 1999; J Clin Oncol 26:1148-1159, 2008]. In addition, the Gynecologic Cancer Intergroup has developed CA-125 progression criteria which are to be integrated with objective tumor assessment for use in first-line trials in ovarian cancer [JNCI 92:1534-1535, 2000].

**Cytology, Histology:** These techniques can be used to differentiate between partial responses (PR) and complete responses (CR) in rare cases (e.g., residual lesions in tumor types, such as germ cell tumors, where known residual benign tumors can remain).

The cytological confirmation of the neoplastic origin of any effusion that appears or worsens during treatment when the measurable tumor has met criteria for response or stable

disease is mandatory to differentiate between response or stable disease (an effusion may be a side effect of the treatment) and progressive disease.

**FDG-PET:** While FDG-PET response assessments need additional study, it is sometimes reasonable to incorporate the use of FDG-PET scanning to complement CT scanning in assessment of progression (particularly possible 'new' disease). New lesions on the basis of FDG-PET imaging can be identified according to the following algorithm:

- Negative FDG-PET at baseline, with a positive FDG-PET at follow-up is a sign of PD based on a new lesion.
- No FDG-PET at baseline and a positive FDG-PET at follow-up: If the positive FDG-PET at follow-up corresponds to a new site of disease confirmed by CT, this is PD. If the positive FDG-PET at follow-up is not confirmed as a new site of disease on CT, additional follow-up CT scans are needed to determine if there is truly progression occurring at that site (if so, the date of PD will be the date of the initial abnormal FDG-PET scan). If the positive FDG-PET at follow-up corresponds to a pre-existing site of disease on CT that is not progressing on the basis of the anatomic images, this is not PD.
- FDG-PET may be used to upgrade a response to a CR in a manner similar to a biopsy in cases where a residual radiographic abnormality is thought to represent fibrosis or scarring. The use of FDG-PET in this circumstance should be prospectively described in the protocol and supported by disease-specific medical literature for the indication. However, it must be acknowledged that both approaches may lead to false positive CR due to limitations of FDG-PET and biopsy resolution/sensitivity.

*Note: A 'positive' FDG-PET scan lesion means one which is FDG avid with an uptake greater than twice that of the surrounding tissue on the attenuation corrected image.*

## 13.4 Response Criteria

### 13.4.1 Evaluation of Target Lesions

**Complete Response (CR):** Disappearance of all target lesions. Any pathological lymph nodes (whether target or non-target) must have reduction in short axis to <10 mm.

**Partial Response (PR):** At least a 30% decrease in the sum of the diameters of target lesions, taking as reference the baseline sum diameters.

**Progressive Disease (PD):** At least a 20% increase in the sum of the diameters of target lesions, taking as reference the smallest sum on study (this includes the baseline sum if that is the smallest on study). In addition to the relative increase of 20%, the sum must also demonstrate an absolute increase of at least 5 mm. (Note: the appearance of one or more new lesions is also considered progression).

**Stable Disease (SD):** Neither sufficient shrinkage to qualify for PR nor sufficient increase to qualify for PD, taking as reference the smallest sum diameters while on study.

### 13.4.2 Evaluation of Non-Target Lesions

**Complete Response (CR):** Disappearance of all non-target lesions and normalization of tumor marker level. All lymph nodes must be non-pathological in size (<10 mm short axis).

*Note: If tumor markers are initially above the upper normal limit, they must normalize for a patient to be considered in complete clinical response.*

**Non-CR/Non-PD:** Persistence of one or more non-target lesion(s) and/or maintenance of tumor marker level above the normal limits.

**Progressive Disease (PD):** Appearance of one or more new lesions and/or unequivocal progression of existing non-target lesions. Unequivocal progression should not normally trump target lesion status. It must be representative of overall disease status change, not a single lesion increase.

Although a clear progression of “non-target” lesions only is exceptional, the opinion of the treating physician should prevail in such circumstances, and the progression status should be confirmed at a later time by the review panel (or Principal Investigator).

### 13.4.3 Evaluation of Best Overall Response

The best overall response is the best response recorded from the start of the treatment until disease progression/recurrence (taking as reference for progressive disease the smallest measurements recorded since the treatment started). The patient's best response assignment will depend on the achievement of both measurement and confirmation criteria.

#### For Patients with Measurable Disease (i.e., Target Disease)

Target Lesions	Non-Target Lesions	New Lesions	Overall Response	Best Overall Response when Confirmation is Required*
CR	CR	No	CR	>4 wks. Confirmation**
CR	Non-CR/Non-PD	No	PR	>4 wks. Confirmation**
CR	Not evaluated	No	PR	
PR	Non-CR/Non-PD/not evaluated	No	PR	

SD	Non-CR/Non-PD/not evaluated	No	SD	Documented at least once >4 wks. from baseline**
PD	Any	Yes or No	PD	no prior SD, PR or CR
Any	PD***	Yes or No	PD	
Any	Any	Yes	PD	

* See RECIST 1.1 manuscript for further details on what is evidence of a new lesion.
 
** Only for non-randomized trials with response as primary endpoint.
 
*** In exceptional circumstances, unequivocal progression in non-target lesions may be accepted as disease progression.
 
Note: Patients with a global deterioration of health status requiring discontinuation of treatment without objective evidence of disease progression at that time should be reported as "symptomatic deterioration." Every effort should be made to document the objective progression even after discontinuation of treatment.
				

#### For Patients with Non-Measurable Disease (i.e., Non-Target Disease)

Non-Target Lesions	New Lesions	Overall Response
CR	No	CR
Non-CR/non-PD	No	Non-CR/non-PD*
Not all evaluated	No	not evaluated
Unequivocal PD	Yes or No	PD
Any	Yes	PD

\* 'Non-CR/non-PD' is preferred over 'stable disease' for non-target disease since SD is increasingly used as an endpoint for assessment of efficacy in some trials so to assign this category when no lesions can be measured is not advised

#### 13.4.4 Duration of Response

**Duration of overall response:** The duration of overall response is measured from the time measurement criteria are met for CR or PR (whichever is first recorded) until the first date that recurrent or progressive disease is objectively documented (taking as reference for progressive disease the smallest measurements recorded since the treatment started).

The duration of overall CR is measured from the time measurement criteria are first met for CR until the first date that progressive disease is objectively documented.

**Duration of stable disease:** Stable disease is measured from the start of the treatment until the criteria for progression are met, taking as reference the smallest measurements recorded since the treatment started, including the baseline measurements.

#### 13.4.5 Progression-Free Survival

PFS is defined as the duration of time from start of treatment to time of progression or death, whichever occurs first.

#### **13.4.6 Overall Survival**

Overall survival is measured from time of diagnosis to time of death.

#### **13.4.7 Response Review**

All responses will be reviewed by an expert independent of the study at the study's completion. Simultaneous review of the patients' files and radiological images is the best approach.

### **14.0 STATISTICAL CONSIDERATIONS**

#### **14.1 Study Design**

This three-step, non-randomized, open-label, phase II trial is designed to explore the efficacy effect of palbociclib in addition to the standard CRT regimen with either cisplatin or cetuximab in patients with p16INK4a negative, HPV-unrelated HNSCC (OP, Larynx, Hypopharynx, and Oral Cavity), Stage III-IV disease. In step one, all patients will be treated with neoadjuvant palbociclib monotherapy for two cycles (28 days per cycle). In step two (CRT), based upon performance status and organ function at enrollment, patients will be assigned to two cohorts: one will be treated with cisplatin and RT over 6 weeks, and the second will be treated with cetuximab and RT over 7 weeks. In step three, all patients in the trial (both cohorts) will be treated with adjuvant palbociclib for six cycles (28 days per cycle) following the completion of CRT.

#### **14.2 Primary Endpoint**

Overall tumor response to neoadjuvant palbociclib monotherapy at the end of step one, a categorical variable (CR, PR, SD, or Progression). Overall tumor response rate is defined as the proportion of subjects who achieve a CR or PR based on RECIST criteria.

#### **14.3 Secondary Endpoints**

- Local-regional disease relapse, a binary variable (Yes vs. No). Local-regional disease relapse rate is defined as the proportion of subjects alive who have local-regional progressed disease at 18 months following completion of CRT.
- Distant metastases, a binary variable (Yes vs. No). Distant metastases rate is defined as the proportion of subjects alive who have distant metastases at 18 months following completion of CRT.
- Progression-free survival (PFS), defined as the days from the start of Step 2 (CRT) to the first documentation of disease progression or death from any cause or the end of follow-up.

- Overall survival (OS), defined as the days from the time of diagnosis to death from any cause or the end of follow-up.

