Based on the controversy surrounding the comparability of these two CRT regimens, current practice at most programs is to route HNSCC patients with excellent performance status and adequate vital organ function to receive CRT with high dose bolus cisplatin. However, it is feasible to administer cetuximab but not cisplatin to a broader mix of patients, particularly those with reduced renal function, poor performance status, and a high comorbidity index. As such, cetuximab has been widely selected over cisplatin to be combined with RT for HNSCC patients with reduced performance status and/or vital organ function.

The efficacy of CRT in patients with locally advanced p16INK4a negative/HPV-unrelated HNSCC is surprisingly modest with a substantial risk of disease recurrence and death. RTOG 0129 and RTOG 91-11 provide reference points for efficacy of CRT using cisplatin. In patients with p16INK4a negative OPSCC, RTOG 0129 found that CRT with cisplatin resulted in three-year OS of 57%, progression-free survival (PFS) 43%, local-regional failure rate 52%, and distant metastasis rate of 16%. In patients with larynx SCC, RTOG 91-11 found that CRT with cisplatin resulted in two-year OS of 74%, DFS 61%, local-regional failure rate 20%, and distant metastases rate of 8%. The poorest outcomes occur in the infrequent subset of patients with hypopharynx SCC where the 5-year OS was 38% and the local-regional and distant failure rate was 60%. The Bonner trial provides reference points for the efficacy of CRT using cetuximab. The two-year local-regional failure rate was 50%, the distant metastases rate was 16%, and the median OS varied based on sub-site: 32 months for larynx SCC, 24 months for p16INK4a negative OPSCC, and 13 months for hypopharynx SCC.

In the pool of patients with p16INK4a negative/HPV-unrelated HNSCC, larynx SCC, and hypopharynx SCC, the majority (> 90%) of relapse events occur within 18 months of completion of CRT using either cisplatin or cetuximab.

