## **2.2 Secondary Objectives**

1. Determine the combined local-regional disease relapse risk and distant metastases risk at 18 months following completion of CRT.
2. Determine the median and two-year PFS and OS (stratified by cohort) of patients treated with the three step sequence of palbociclib monotherapy, CRT, and adjuvant palbociclib monotherapy.

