### **3.1.2 Additional Cohort 2 Eligibility Criteria**

Patients enrolling to Cohort 2 must meet at least one of the following criteria:

1. ECOG performance status of 2 (see Appendix A)
2. Reduced organ function defined as:
  - a. Creatinine clearance 30-75 mL/min; or
  - b. Bilirubin 1.5-2  $\times$  IULN; or
  - c. ALT and AST 2.5-5  $\times$  IULN

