### **5.3.6 Assessments after Completion of CRT**

1. Office FOE and CT neck (with IV contrast) and CT chest (or CXR) at 8, 12, 18, 24, 30, 36, 42, 48, 54, and 60 months (+/- 1 month) after completion of CRT [FOE will be conducted as standard of care after 12 months of follow-up, so they will occur at some, but not all, of the long-term follow-up visits]
2. Documentation of presence of PEG tube or tracheostomy tube at the same monitoring intervals.
3. Documentation of weight (Kg) at the same monitoring intervals.
4. QOL assessments at the same monitoring intervals.
5. Study Lab collection of 3 green top tubes for PBMC at 4 months (+/- 1 month) after completion of adjuvant treatment (4 months post step 3).

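### The 18-month local-regional relapse and distant-metastasis rates are defined on subjects alive, so a patient who relapses and dies earlier is not counted, although the objective asks for the risk

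*Combined protocol and SAP*

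**What the plan says.** The first secondary objective (Section 2.2) reads: "Determine the combined local-regional disease relapse risk and distant metastases risk at 18 months following completion of CRT". It asks for a risk and contains no restriction to survivors.

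Section 14.3 turns this into two endpoints. The first begins "Local-regional disease relapse, a binary variable (Yes vs. No"), again unrestricted, but the rate derived from it is "defined as the proportion of subjects alive who have local-regional progressed disease at 18 months following completion of CRT". The second follows the same pattern: "Distant metastases rate is defined as the proportion of subjects alive who have distant metastases at 18 months following completion of CRT".

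Section 14.6.2 adds only that each rate is reported with a 95% confidence interval, separately by cohort. Section 14.6 says that data are evaluated as observed without imputation, and that all analyses are exploratory. No section names a cumulative-incidence or competing-risk method for these rates, or says how to classify a patient who relapsed and then died before 18 months.

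**The concern.** A risk by 18 months counts everyone who has had the event by then, dead or alive. The Section 14.3 wording counts only people who are alive at 18 months with the event. Someone who relapses at month 6 and dies at month 12 is exactly the outcome the objective is about, and is not counted as a relapse.

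Such patients are unlikely to be rare here. Section 1.2 says that "the majority (> 90%) of relapse events occur within 18 months of completion of CRT using either cisplatin or cetuximab". For cetuximab with RT it reports that "the median OS varied based on sub-site: 32 months for larynx SCC", with 24 months for p16-negative oropharynx and 13 months for hypopharynx. Relapse is expected early, and a material fraction of patients may be dead by month 18.

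The sentence can also be read in two ways, which give different numbers from the same patients. PFS does not fill the gap: it counts every death but does not separate local-regional from distant failure. Section 14.5 says that the trial is to inform future confirmatory trials, so understated failure rates could be carried forward as planning values.

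**Working it through.** The plan states no target or expected value for these two rates, so there is no figure of its own to reproduce. The check compares what each reading estimates with what the objective asks for.

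**Notation (assumptions unless a source is given)**
- R = true risk of the event by 18 months. Section 1.2 gives reference failure rates, on other clocks and in other populations: local-regional 20% (larynx, cisplatin), 50% (cetuximab) and 52% (oropharynx, cisplatin); distant 8% and 16%.
- f = share of patients with the event who are dead by 18 months. Not in the documents.
- g = share of patients without the event who are dead by 18 months. Not in the documents.
- n = 24, both cohorts together (Section 14.4).

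**What each reading estimates**
- Objective: R.
- All-subjects reading (alive with the event, over everyone): R(1 − f). The shortfall is R·f, which is positive whenever any relapsed patient has died.
- Survivor reading (alive with the event, over those alive): R(1 − f) / [R(1 − f) + (1 − R)(1 − g)]. This is below R if and only if f > g, equal to R if f = g, and above R if f < g.

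**Count example:** 24 patients, 12 relapse, 6 of those die by 18 months, 1 other patient dies without relapse. Intervals are exact (Clopper-Pearson) 95%.

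| Quantity | Count | Estimate | 95% CI |
|---|---|---|---|
| Risk (objective) | 12/24 | 50% | 29–71% |
| Survivor reading | 6/(24 − 6 − 1) = 6/17 | 35% | 14–62% |
| All-subjects reading | 6/24 | 25% | 10–47% |

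**Range of the shortfall**, in percentage points, over f = 30–70% and g = 5–25%

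| R | Survivor reading | All-subjects reading |
|---|---|---|
| 8% | 0.5 to 5.3 | 2.4 to 5.6 |
| 16% | 0.9 to 10.3 | 4.8 to 11.2 |
| 20% | 1.1 to 12.7 | 6 to 14 |
| 30–50% | 1.4 to 26 | 9 to 35 |

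For the survivor reading the smallest shortfall in each row is at f = 30%, g = 25%. At R = 30%: 0.30 × 0.70 / (0.30 × 0.70 + 0.70 × 0.75) = 0.21/0.735 = 28.6%, a gap of 1.4. The largest is at f = 70%, g = 5%. At R = 50%: 0.15/(0.15 + 0.475) = 24.0%, a gap of 26.

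**When the survivor reading does not understate**
- f = g: 12 relapses with 3 deaths among relapsed and 3 among non-relapsed patients gives 9/18 = 50%, no bias.
- f < g: R = 40%, f = 20%, g = 30% gives 0.32/(0.32 + 0.42) = 43%, too high.

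**Is early death plausible?** If survival were exponential with the medians in Section 1.2, the share dead at 18 months would be 1 − 0.5^(18/13) = 62%, 1 − 0.5^(18/24) = 41% and 1 − 0.5^(18/32) = 32%. Those medians are for all patients on the reference trial's own clock, not from completion of CRT. They show that deaths by 18 months may be common, not that f exceeds g.

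**The case against.** Four points can be made for the plan.

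- **The stakes are low.** The two rates are descriptive secondary endpoints in a trial that calls all its analyses exploratory. No test of efficacy, sample size or stopping rule uses them, and patients who relapse and die still count in PFS and OS. This stands and limits the severity. It does not make the definition match the objective.
- **The direction is not proven under the survivor reading.** Section 1.2 does not separate deaths in relapsed patients from deaths in the others. Cohort 2 admits patients with "ECOG performance status of 2" or reduced organ function, so deaths without relapse may not be rare there. This stands: f > g is plausible, but it is an assumption. Only the all-subjects reading is certain to be low once a relapsed patient has died.
- **Sampling error is as large as the bias.** The example intervals overlap heavily, and reporting by cohort makes the denominators smaller still. This also stands, but more patients would narrow the interval around the wrong quantity.
- **The Yes/No variable carries no restriction.** That is so, and the coding of relapse for the biomarker tests in Section 14.6.2 is therefore unstated rather than wrong. The reported rate, however, has its own explicit definition, and the restriction appears in both rate definitions.

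**Conclusion.** The concern holds. Followed as written, Section 14.3 does not estimate the risk that Section 2.2 asks for, and its wording allows two different answers from the same data. That conclusion rests on the text alone.

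The size rests on assumed values of R, f and g. At true risks of 30–50% the shortfall could be anywhere from about 1 to 26 points on the survivor reading and 9 to 35 points on the all-subjects reading. It is smaller at the lower distant-metastasis rates. On the survivor reading it vanishes or reverses if relapsed patients do not die more often than the others.

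This should be fixed before analysis, but it is not a threat to the trial: the primary endpoint, PFS, OS and the monitoring rules are unaffected.

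**What to change.** **Minimum change.** In both rate definitions in Section 14.3, delete the word alive and define the numerator as subjects who have had the event by 18 months after completion of CRT. This removes the contradiction.

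**Preferred change.** In Sections 14.3 and 14.6.2, define each endpoint as the cumulative incidence by 18 months after completion of CRT of first local-regional relapse and, separately, of distant metastasis. Count every event whether or not the patient later died, treat death without that event as a competing risk, and censor patients lost to follow-up at their last disease assessment. Keep the report by cohort.

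**To settle in the same edit**
- How many enrolled patients did not complete CRT and so have no starting point for this clock.
- What combined means in the first secondary objective; if it means either event, use the same estimator for it.
- That the biomarker tests in Section 14.6.2 code relapse as an event by 18 months, alive or dead.

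**Cost.** The minimum change is wording only. The preferred one also needs event dates and the censoring rule written down. No new data are required: Section 5.3.6 already plans "CT neck (with IV contrast) and CT chest (or CXR) at 8, 12, 18, 24" months and later, and deaths go on the Death Form (Section 12.1). One check is worthwhile: the Section 10.2 calendar lists neck CT at these visits and mentions the chest only in its 8-month footnote, so it should be aligned with Section 5.3.6, on which detection of distant metastases depends. The reported rates will probably look less favourable.

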### **5.0 TREATMENT PLAN**

“The three step” trial is a two cohort, non-randomized phase II trial in which palbociclib will be integrated into the standard CRT regimen with either cisplatin (cohort 1) or cetuximab (cohort 2). Patients with stage III-IV (non-metastatic) p16INK4a negative, HPV-unrelated HNSCC will be enrolled, to enrich the fraction of patients most likely to benefit from a CDK4/6 inhibitor.

During step one, patients in both cohorts will be treated with neoadjuvant palbociclib monotherapy (125 mg/day, Days 1-21 of a 28-day cycle for two cycles). A CT scan of the neck to assess tumor response and a tumor biopsy for pharmacodynamics assessment will be performed before and after palbociclib (CT scan – Cycle 2 post-treatment Day 21 through Day 25; Tumor biopsy Cycle 2 Day 21). Data will be pooled from the two cohorts to address the primary aim. The primary aim of the trial is to determine the tumor response rate (using RECIST 1.1) of newly diagnosed p16INK4a negative, HPV-unrelated HNSCC to palbociclib monotherapy given over two cycles, and to explore potential pharmacodynamic determinants of tumor response to palbociclib monotherapy using data derived from genomic, RNA, and protein expression methods performed on pre- and post-treatment tumor tissue.

During step two (CRT), Cohort 1 patients will be treated with cisplatin 100 mg/m^2 given on Days 1 and 22 with RT. Cohort 2 patients will be treated with cetuximab given one week before RT and then weekly during RT. Cohorts 1 and 2 will receive accelerated IMRT 70 Gy to be administered over 6 weeks in once daily fractions Monday through Friday, with one additional fraction of RT administered on (preferably) Fridays. The two fractions administered on one day will be at least 6 hours apart. Palbociclib, an oral agent, will not be given during step two due to the severe difficulty with swallowing that occurs in all patients treated with CRT and due to the lack of feasibility

studies for this combination therapy. To assess overall tumor response (stratified by cohort), a CT scan of the neck will be performed 8-10 weeks following completion of CRT, and FDG-PET/CT will be performed 14-18 weeks following completion of CRT.

During step three, patients in both cohorts will be treated with adjuvant palbociclib 125 mg/day, days 1-21 of each 28-day cycle for six cycles. Adjuvant palbociclib will begin 16 to 22 weeks following completion of CRT.

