## 13.0 MEASUREMENT OF EFFECT

### 13.1 Antitumor Effect – Solid Tumors

For the purposes of this study, patients should be re-evaluated for response every 8 weeks. In addition to a baseline scan, confirmatory scans should also be obtained not less than 4 weeks following initial documentation of objective response.

Response and progression will be evaluated in this study using the new international criteria proposed by the revised Response Evaluation Criteria in Solid Tumors (RECIST) guideline (version 1.1) [Eur J Ca 45:228-247, 2009]. Changes in the largest diameter (unidimensional measurement) of the tumor lesions and the shortest diameter in the case of malignant lymph nodes are used in the RECIST criteria.

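### Viable tumour that persists after chemoradiation without growing, or is resected before it grows, is not itself a local-regional or PFS event under Sections 14.3 and 13.4.5

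*Combined protocol and SAP*

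**What the plan says.** - **Section 14.3, local-regional relapse:** "the proportion of subjects alive who have local-regional progressed disease at 18 months following completion of CRT".
- **Section 14.3, PFS:** time from the start of CRT to "the first documentation of disease progression or death from any cause or the end of follow-up".
- **Section 13.4.5, PFS:** "PFS is defined as the duration of time from start of treatment to time of progression or death, whichever occurs first". The two PFS definitions start the clock at different points, which is a separate matter. They agree on what counts as an event: progression or death.
- **Section 13.1:** "Response and progression will be evaluated in this study using the new international criteria proposed by the revised Response Evaluation Criteria in Solid Tumors". No other criteria are given for failure after CRT.
- **Section 13.4.1, progression in target lesions:** "At least a 20% increase in the sum of the diameters of target lesions", measured from the smallest sum on study and with an absolute rise of at least 5 mm. A new lesion also counts, as does clear progression of non-target disease (13.4.2).
- **Section 5.0:** a neck CT is done 8-10 weeks after CRT, and "FDG-PET/CT will be performed 14-18 weeks following completion of CRT". The stated purpose of both is to assess tumour response.

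No section names persistent disease, biopsy-proven residual tumour or surgery after CRT as an event, and none gives a censoring rule for them.

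**The concern.** RECIST progression asks whether tumour has grown. After treatment given with curative intent, the clinical question is also whether tumour has cleared. A patient with viable cancer left at the primary or in a neck node has not been controlled locally, even if the mass is smaller than at baseline. Under the plan that patient is a partial response or stable disease. If the residual tumour is then resected before it grows, nothing that happened is an event for either endpoint.

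The secondary objectives in 2.2 ask how often the three-step sequence fails locally and distantly and how long patients remain progression-free. Section 14.5 intends the results as baseline information for later confirmatory trials. An event definition that omits one kind of failure moves both results in the favourable direction. Persistence that is left in place is eventually counted if it regrows, but it is dated at the regrowth and not when viable tumour was first shown, which also lengthens PFS.

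**Working it through.** The plan states no event count, precision or power for these secondary endpoints, so there is no figure to reproduce. The check is a trace of the definitions, then arithmetic on how much one patient matters.

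**1. RECIST scoring of residual tumour.** The progression threshold is the larger of 1.2 × smallest sum and smallest sum + 5 mm (13.4.1). The sizes below are illustrative.

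| Baseline sum | Residual after CRT | Change | Score | Progression only at |
|---|---|---|---|---|
| 50 mm | 20 mm | (20 − 50)/50 = −60% | PR | max(24, 25) = 25 mm |
| 50 mm | 40 mm | (40 − 50)/50 = −20% | SD | max(48, 45) = 48 mm |

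If either tumour is removed at its residual size, the threshold is not met. There is no local-regional progression to report at 18 months, and PFS continues until a later regrowth, new lesion, death or end of follow-up.

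**2. Does another rule catch these patients?**
- *PET (13.3).* The algorithm for finding new lesions covers a negative baseline PET and a missing baseline PET. Sections 5.3.1 and 10.1 schedule a baseline FDG-PET/CT, and 3.1 requires measurable disease. There is no branch for a site that is positive at baseline and still positive at 14-18 weeks.
- *Endoscopy and biopsy (13.3).* These are not advised for objective tumour evaluation. The stated exception covers recurrence after complete response or resection. Tumour that never cleared does not fit the first case, and 14.3 does not take up the exception.
- *Data capture (12.0).* RECIST forms are due at 8-10 weeks and then from 8 months. None is due at the 14-18 week PET/CT, and no form is listed for pathology or surgery after CRT.

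**3. Weight of one patient.** The endpoint is a proportion of subjects alive at 18 months, with at most 24 in the denominator (14.4). One affected patient who is alive then adds 1/n, with n ≤ 24:
- all patients: 1/24 = 4.2 points at least;
- a cohort of 12: 1/12 = 8.3 points. The 12/12 split is an assumption; 14.4 gives only the total, but 14.6.2 analyses by cohort.

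**4. Sensitivity.** The documents give no rate of persistence or of resection, so the number of uncounted failures is set at 0 to 4 as an assumption. The starting counts, 5 and 12 of 24, are chosen to lie near the low and high local-regional failure rates in Section 1.2 (20% and 52%). Intervals are exact 95%.

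| Uncounted failures added | Starting from 5/24 | Starting from 12/24 |
|---|---|---|
| 0 | 20.8% (7.1-42.2) | 50.0% (29.1-70.9) |
| 1 | 25.0% (9.8-46.7) | 54.2% (32.8-74.4) |
| 2 | 29.2% (12.6-51.1) | 58.3% (36.6-77.9) |
| 3 | 33.3% (15.6-55.3) | 62.5% (40.6-81.2) |
| 4 | 37.5% (18.8-59.4) | 66.7% (44.7-84.4) |

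**The case against.** **RECIST is not named in 14.3 for these endpoints.** It is named for the primary endpoint (14.2) and the interim look (14.7), but for relapse and PFS the link is the general sentence in 13.1. The label relapse, with laryngoscopy at 8-10 weeks and in follow-up, leaves an investigator room to record persistent tumour as a failure. That is fair, but no rule tells the investigator to do so. In an open-label trial, leaving it to individual judgement is itself a weakness.

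**Counting PR and SD as progression-free is ordinary RECIST practice.** It is, and residual tumour will be visible in the response data at 8-10 weeks. It will not be visible in the two endpoints that are meant to describe failure.

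**A reader might infer that 13.3 expressly rules residual uptake out**, because it says that uptake which "corresponds to a pre-existing site of disease on CT that is not progressing on the basis of the anatomic images, this is not PD". The documents do not support this. That sentence belongs to the branch for patients without a baseline PET. For patients with one, the text is silent.

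**A reader might infer that these patients can never have an event.** That is too strong. Death, regrowth or a new lesion still counts for PFS, and local regrowth present at 18 months counts for relapse.

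**The endpoints are secondary and exploratory.** Section 14.6 says so of all analyses, and no test against the rates in 1.2 is planned. In the table, adding up to four patients leaves the estimate inside the starting interval. This limits the importance of the point, but a systematic shift is not excused by a wide interval.

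**Ascertainment would depend on care.** No biopsy is scheduled after CRT, so confirmed persistence would be found only where routine care obtains tissue. This stands as a limit of the remedy.

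**Conclusion.** The point holds as a gap in the event definitions. As written, viable tumour that persists after CRT without growing, and resection of that tumour, are not local-regional or PFS events. Compared with counting them, the rule can only lower the relapse rate and lengthen PFS.

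The size is unknown. The documents do not say how often tumour persists after CRT or is resected, and they do not mention salvage surgery, so it cannot be claimed that this is common. What can be said is the weight per affected patient alive at 18 months: at least 4.2 points overall, and 8.3 points if a cohort has 12.

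A reader might also infer that the trial's rate would look better than the reference rates in Section 1.2 for this reason alone. Whether the reference trials counted persistence cannot be settled from these documents. The primary endpoint and the interim rules are unaffected. The change is worth making because it is cheap and removes a bias of known direction.

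**What to change.** In 14.3, with matching words in 13.4.5, add for endpoint scoring only:

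- Pathology-proven viable tumour at the primary or neck, from a biopsy or resection done in routine care at or after the 8-10 week CT or the 14-18 week PET/CT, is a local-regional failure and a PFS event, even without RECIST growth.
- The event date is the first positive assessment that the pathology confirms.
- For the 18-month proportion, such a failure counts if it occurred by then, whether or not the tumour has since been removed. Otherwise the present status-at-18-months wording would drop the resected patient again.
- The finding and its date are recorded on the follow-up form.

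State alongside this that the scoring does not alter the RECIST progression criteria in 13.3-13.4 or the treatment-discontinuation rule in 5.7, which turns on documented progression after Step 2. Without that sentence, a change to an endpoint could be read as a change to treatment.

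The cost is definition wording and a data field, with no added procedure. The reported relapse rate and PFS may become somewhat less favourable. Because tissue is obtained only in routine care, some persistence will still go unconfirmed, and the report should say so.
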